5.2 Reduction of Bias

Measures proposed to limit bias include making the LACTIN-V and placebo applicators similar in appearance. Both study personnel and the subject will be completely blinded to the random treatment assignment.

6 STUDY MATERIALS AND METHODS

6.1 Study Materials

6.1.1 LACTIN-V and Placebo Applicators

Each LACTIN-V applicator contains 200 mg of LACTIN-V powder with 2 x 10⁹ CFU of *L. crispatus* CTV-05. The LACTIN-V powder formulation also contains maltodextrin, xylitol, trehalose, and sodium ascorbate. LACTIN-V placebo applicators contain 200 mg of the powder formulation without *L. crispatus* CTV-05.

6.1.2 LACTIN-V

6.1.2.1 Background

The Medicines Company originally licensed world-wide rights to a proprietary organism, *Lactobacillus crispatus* strain CTV-05, which had undergone clinical development as an adjunctive treatment for vaginal infections (Lactin-Vaginal). Acquired in 1999 from a small biotech company, GyneLogix, Inc., in Louisville, Colorado, the product had been developed in conjunction with the NIH through completion of a Phase 2 study. The

Medicines Company elected a strategic direction focusing on acute care products sold to hospitals and this led to a decision to out-license rights to continued development of this product to Osel, Inc.

6.1.2.2 The Product

LACTIN-V contains *Lactobacillus crispatus* CTV-05 bacteria preserved by lyophilization in a simple freeze drying medium. CTV-05 is a strain of *Lactobacillus crispatus*, a gram-positive rod isolated from the vagina of a healthy woman. *Lactobacillus crispatus* is found naturally in the vaginas of healthy women and is commonly found as a component of the natural human intestinal microbiota. It is a facultative anaerobe, homofermentor of lactic acid, fastidious in its growth, and capable of H₂O₂ production. Unlike most commercially available strains of *Lactobacillus*, CTV-05 adheres well to epithelial cells and is thus able to colonize the vaginal epithelium. The powder is loaded into an applicator for vaginal administration. The filled applicator is packaged under nitrogen with desiccant in a Mylar foil pouch. The manufacturing and formulation of this organism are carried out in a proprietary process.

6.1.2.3 Manufacturing and Packaging Information

LACTIN-V contains *Lactobacillus crispatus* CTV-05 bacteria preserved by spray drying with a simple drying medium. *Lactobacillus crispatus* is a naturally occurring organism isolated from the vagina of a healthy woman in 1993. The final product appears as an off-white to light yellow powder, which is delivered as a vaginal applicator. The applicators pre-filled and individually packaged.

6.2 Study Methods

6.2.1 Subject Selection

6.2.1.1 Recruitment

The volunteers for this study will be recruited from Hall Health Primary Care Center at the University of Washington (Seattle, WA), as well as thru posted flyers and UW Daily Ads. The study will follow Health Insurance Portability and Accountability Act (HIPAA) guidelines where applicable.

6.2.1.2 Eligibility

6.2.1.2.1 Inclusion Criteria

1. Pre-menopausal women aged 18–45 years of age at date of the Screening Visit.

2. Meets criteria for current symptomatic acute uncomplicated cystitis, defined as one or more UTI symptoms (dysuria, urgency, frequency, suprapubic pain), and pyuria (>10 wbc) on hemocytometer count, confirmed with a positive urine culture with greater than 10^2 /ml of an uropathogen.
3. Completion of all screening procedures. Screening will take place at the visit at which acute uncomplicated cystitis (UTI) diagnosis is made.
4. History of one Symptomatic UTI episode treated within the past 12 months.
5. Agree to return for the Randomization Visit (Visit 1) within 3–10 days of completing antibiotic treatment for UTI.
6. Regular menstrual cycles (21–35 days) or amenorrheic due to birth control method. Women using IUD(C) must be 2 months post insertion of IUD.
7. Subject is willing to insert vaginal applicators.
8. Capable of providing informed consent.
9. Able to read and understand English.
10. Agree to abstain from self-medication with antibiotics for UTI symptoms.
11. Agree to abstain from antibiotic prophylaxis for recurrent UTI.
12. Agree to abstain from the use of any other intra-vaginal product (i.e., contraceptive creams, gels, foams, sponges, lubricants, douches, etc.).
13. Agree to abstain from sexual intercourse for 24 hours after each applicator is inserted.
14. Agree to not use tampons for 24 hours after each applicator is inserted.
15. Agree to use an adequate method of birth control throughout study to avoid pregnancy. Acceptable methods include bilateral tubal-ligation, male partner with a vasectomy, steroidal contraceptive (oral, patch, injectable, implantable), IUD, condoms (to be provided), or abstinence. If condoms are used, they should be non-spermicidal condoms provided by the site.

6.2.1.2.2 Exclusion Criteria

1. Complicated cystitis or pyelonephritis (uncomplicated or complicated)
2. Vaginal or cervical infection, currently or within the past 30 days, with bacterial vaginosis (treated, symptomatic infection), yeast, *Trichomonas vaginalis*, *Neisseria gonorrhoeae*, *Chlamydia trachomatis* or genital Herpes simplex.

3. Symptomatic BV and/or yeast at Visit 1 (women who have Asymptomatic BV at Visit 1 may participate in the study).
4. High risk for sexually transmitted diseases and/or HIV, including: diagnosis of *N. gonorrhoeae*, *C. trachomatis* or *T. vaginalis* on two or more occasions during the previous six months;
5. History of chronic vaginal, urinary or pelvic symptoms not attributable to UTI.
6. Pregnancy or within two months of last pregnancy (all subjects must have a negative urine pregnancy test prior to randomization).
7. Lactation.
8. Antibiotic therapy (vaginal or systemic) less than three days prior to Randomization Visit (Visit 1).
9. Antifungal therapy (vaginal or systemic) less than thirty days prior to the Randomization Visit.
10. Antibiotics planned within four months (including prophylactic antibiotics).
11. Investigational drug use within 30 days or current participation in any urogenital studies.
12. Menopause.
13. Any significant disease or acute illness that in the Investigator's assessment could complicate the evaluation.
14. Known HIV infection.
15. Immunosuppressive drug within 60 days.
16. Known allergy to any component of LACTIN-V or the placebo capsule.
17. Unavailable for follow-up visits.
18. Have any social or medical condition that, in the opinion of the Investigator, would preclude provision of informed consent, make participation in the study unsafe, complicate interpretation of study outcome data, or otherwise interfere with achieving the study objectives.

Subjects who develop the following exclusion criteria while on study will discontinue study treatment, but continue to be followed for safety and efficacy endpoints whenever possible.

- Pregnancy
- Lactation
- HIV infection
- Treatment with immunosuppressive drug
- Allergy to LACTIN-V or placebo capsule

Subjects who develop any other exclusion criteria while on study will be managed at the discretion of the Investigator, in consultation with the Medical Monitor.

6.2.1.3 Screening Failures and Subject Replacement

Volunteers with the following diagnoses at Visit 1 will be considered screening failures and will be treated or referred for appropriate follow-up. All screening failures will be replaced.

1. Complicated cystitis or uncomplicated or complicated pyelonephritis.
2. Abnormal findings on pelvic examination that would interfere with the evaluation of safety.
 - a. Unable to visualize cervix.
 - b. Clinically significant inflammation, erosions and/or petechiae of external genitalia, vagina or cervix on visual examination.
 - c. Clinically significant tenderness on bimanual examination.
3. Evidence of a sexually transmitted disease.
4. Symptomatic BV or yeast.

6.2.1.4 Withdrawal of Randomized Subjects

Study subjects who have been randomized may be withdrawn from receiving further investigational product for the following reasons:

1. Allergy to the study product.
2. Adverse event.
3. Unable or unwilling to use LACTIN-V applicators for the duration of the study.
4. Failure to follow protocol requirements that would significantly affect study outcomes.
5. Pregnancy.
6. Medical reasons unrelated to study products. This determination will be at the discretion of the Investigator, but might include major new diagnoses such as a malignancy requiring chemotherapy.
7. Personal reasons (voluntary request or withdrawal of consent).
8. Physician decides that it is not in the best interest of the subject to continue participation.
9. Physician or sponsor decides, for whatever reason, to discontinue the study.

For randomized subjects who are withdrawn from receiving further product, the site will make every effort to continue to follow all subjects for efficacy through duration of study.

6.2.1.5 Discontinuation and Subject Replacement

The study subject may choose to leave the study at any time. Reasons for leaving the study will be recorded. Study subjects who enroll in the study but who do not return after three attempts to contact them will be considered study “lost to follow-up”.

Once a subject is randomized, she will not be replaced. Withdrawals and drop-outs will not be replaced.

6.2.2 Blinding and Unblinding of Treatment Assignment

6.2.2.1 Blinding

The most important factor for the success of a blinded study is to maintain the blind throughout the entire course of the trial. In this study, the treatment assignment to LACTIN-V and the placebo applicator will be maintained by [name], M.S., the study statistician. Treatment assignment will be blinded to all other study staff and subjects.

The study product will be prepackaged in accordance with a previously generated randomization schedule. It will be supplied to the study site labeled only with the Protocol Number and Subject Number. As study product is shipped to the sites, a list of Subject Numbers that corresponds to the study product will be enclosed.

A block size of four has been chosen to minimize the potential imbalance between LACTIN-V and placebo. Within each block, subjects will be randomized in a 1:1 ratio to receive either LACTIN-V or placebo. Subjects will be randomized on site in sequential order based on the list of Subject Numbers provided to the site. Lists will not have any treatment assignment associated with the Subject Number.

Applicators will be individually packaged. No one involved in the conduct of the trial will be aware of the specific treatment allocated to any particular subject. Only authorized persons, including the study statistician, will have access to treatment assignments in case of necessary unblinding (see below). The LACTIN-V applicator cannot be distinguished from the placebo applicator (appearance or smell) either before or during administration.

6.2.2.2 Unblinding

Breaking the blind on an individual basis should be considered only when knowledge of the treatment assignment is considered essential by the subject's physician for her care. In the event of an emergency situation for which knowledge of the treatment assignment is necessary for clinical management, the site should notify the Medical Monitor or Clinical Program Manager. Any unintentional unblinding should be reported immediately to [name]. documented during the trial, and reported and explained at the end of the trial in a study report, irrespective of the reason for its occurrence.

6.2.2.3 Unblinding Procedure

Tamper-proof envelopes containing treatment group assignment for each Subject Number will be available to [name], M.S. The tamper-proof envelopes will be stored in a secured location for emergency unblinding purposes only. If the Investigator determines that a subject has experienced a significant adverse event that may be related to the study product and requires unblinding in order to make patient care decisions, he or she should notify the Medical Monitor and Clinical Program Manager immediately. A Request for Emergency Unblinding Form, with the Subject Number, date, time, person making the request, description of the serious adverse event, onset date, and the reasons for unblinding, will be faxed to the Medical Monitor and Clinical Program Manager for review. If unblinding is approved, an authorized person at the University of Washington will open the tamper-proof envelope for the individual subject and promptly report the treatment assignment to the Investigator. In the event that the Medical Monitor or Clinical Program Manager cannot be reached quickly, the Investigator will be provided with a list of representatives who may be contacted to request emergency unblinding. An emergency unblinding log will be maintained by University of Washington.

6.3 General Procedures

6.3.1 Informed Consent

Women who attend a study clinic (or referring clinic) for urinary symptoms and are diagnosed with acute, uncomplicated UTI (including acute uncomplicated cystitis) will be advised that a study is underway. They will be asked if they would like to hear more about the research. If they are interested, written informed consent will be obtained from each study subject prior to commencing any procedure or assessment associated with the Screening Visit (Visit 0). Study subjects will receive a copy of the signed and dated Informed Consent Form (ICF). If the ICF is altered during the study, subjects will be re-consented with the IRB-approved revised ICF, and a copy of the new signed consent form will be provided to the subject.

6.3.2 Confidentiality of Records

Informed consent forms, contact information, and other data collection instruments containing personal identifiers will be securely stored separately in locked offices located at the project site. Only limited study site staff will have access to these files. Only a study identification number will identify the subject in research records. All data will be encoded and entered into a computer using the Subject ID.

6.3.3 Visit 0

Visit 0 is the Screening Visit. This visit is conducted at the time of the UTI diagnosis.

- Visit 0 will occur on the day that the UTI is diagnosed.

Each woman who agrees to be screened will be asked to sign the informed consent form written in English. The screening process will be explained to interested women and written informed consent will be obtained from each woman who agrees to participate. The subject will be asked to provide either a contact phone number or email address, which will be recorded on a subject contact information form. This will be used to remind subjects of follow-up visits.

Women who give informed consent to enrollment will undergo the following procedures and assessments at Visit 0:

1. Detailed structured interview to obtain medical and sexual history. This will include assessment of STD and HIV risk.
2. Review eligibility criteria.
3. Vital signs and weight.
4. Clean catch urine dipstick performed in clinic, with urinalysis, culture and susceptibility testing sent to research laboratory.
5. The subject will then undergo a physical examination and focused genital examination by a study physician or nurse..
6. Pelvic examination, to be conducted in the following order:
 - a. Examination of the external genitalia
 - b. Vaginal swab for pH, wet mount (clue cells and trichomonas), KOH and amine test (whiff test) performed in clinic.
 - c. Swab of vaginal fluid to be stored for assessment of vaginal microbiota by DNA amplification.

Women diagnosed with any symptomatic vaginitis at Visit 0 will be treated and excluded from the study.

6.3.4 Visit 1

Visit 1 is the Randomization Visit. This visit will be scheduled if urine culture confirms the presence of a uropathogen in quantity greater than or equal to 10^2 /ml.

- Visit 1 must occur within 3–10 days of completing the antibiotic, and after the subjects' anticipated menses.

It is possible that the entry UTI episode will not be fully resolved at the time of randomization (Visit 1), as mild symptoms may still be present, and the dipstick and urinalysis may still be slightly positive or equivocal several days after completing antibiotics.

The following procedures and assessments will be performed at Visit 1:

1. Eligibility confirmed.
2. All baseline symptoms to be recorded on the CRF.
3. Urine pregnancy test performed in clinic.
4. Clean catch urinalysis and culture.
5. Vital signs.
6. Pelvic examination, to be conducted in the following order:
 - a. Examination of the external genitalia
 - b. Speculum insertion and examination of vagina, fornices and cervix with naked eye. Only water must be used to lubricate the speculum at all study visits. Other lubricants could kill *L. crispatus*.
 - c. Vaginal swab for pH, wet mount (clue cells), KOH and amine test (whiff test) performed in clinic.
 - d. Vaginal swab for gram stain Nugent score.
 - e. Vaginal swabs for culture (total lactobacilli and *E. coli*) and rep-PCR.
 - f. Swab of vaginal fluid to be stored for assessment of vaginal microbiota by DNA amplification.
 - g. Bimanual examination
7. Subject randomized.
8. First investigational applicator inserted under supervision.
9. Instructions provided to subject regarding:

- a. Study Diary
- b. Dates for initial 5 day applicator use and weekly applicator use will be marked on the Study Calendar, and staff will review with the subject how to record. If subject experiences unanticipated menses she may defer scheduled applicator use and will then record the day of actual use.

6.3.5 Visits 2 thru 5

The following procedures and assessments will be performed at follow-up Visits 2 thru 5 (unless otherwise specified):

1. All reported AEs to be recorded on the AE CRF.
2. Clean catch urine dipstick performed in clinic.
3. Urinalysis and urine culture.
4. Urine pregnancy test performed in clinic only if clinically indicated.
5. Focused physical examination, if indicated for assessment of symptoms and adverse events.
6. Pelvic examination to be conducted in the following order:
 - a. Examination of the external genitalia.
 - b. Vaginal swab for pH, wet mount (clue cells), KOH and amine test (whiff test) performed in clinic.
 - c. Vaginal swabs for culture (total lactobacilli and *E. coli*) and rep-PCR sent to laboratory
 - d. Vaginal swab for gram stain Nugent score sent to laboratory (Visit 5 only).
 - e. Swab of vaginal fluid to be stored for assessment of vaginal microbiota by DNA amplification.
7. All diagnoses of UTI are to be recorded on the UTI CRF.

Subjects diagnosed with Symptomatic UTI during study participation are to be treated as clinically indicated and should continue to use study applicators as scheduled.

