3.2.2 Secondary Objectives

1. To evaluate vaginal colonization with total *Lactobacillus* (endogenous and exogenous) in subjects receiving LACTIN-V versus placebo.
2. To evaluate vaginal colonization with *Lactobacillus crispatus* strain CTV-05 (the LACTIN-V strain of *Lactobacillus*).
3. To evaluate vaginal colonization with *E. coli* in subjects receiving LACTIN-V versus placebo.
4. To evaluate shifts in vaginal microbiota in subjects receiving LACTIN-V versus placebo, as assessed by Nugent score of vaginal gram stains at all visits.

5. To evaluate shifts in the composition of vaginal microbiota in subjects receiving LACTIN-V versus placebo, as assessed by qualitative and/or quantitative DNA amplification of stored vaginal fluid specimens from all visits.
6. To evaluate the safety of LACTIN-V over four months.

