4.3 Rationale for Study Design

The study will enroll 276 pre-menopausal women currently with a symptomatic UTI who report at least one other symptomatic UTI episode treated within the past 12 months. Subjects will be randomized to receive either LACTIN-V (5×10^9 CFU/applicator) or a placebo applicator in a 1:1 ratio. The Randomization Visit (Visit 1) must occur within 3–

10 days of completing antibiotics since the vaginal microbiota is thought to be maximally disrupted at this time, thus providing *L. crispatus* CTV-05 the best chance of successful colonization.

It is not anticipated that the entry UTI episode will necessarily have fully resolved at the time of randomization (Visit 1), as mild symptoms may still be present, and the dipstick and urinalysis may still be positive or equivocal several days after completing antibiotics. However, the urine culture is anticipated to be negative at Visit 1, following completion of antibiotics; therefore, subjects with a positive urine culture at this visit will be considered an antibiotic treatment failure.

All subjects will return to clinic at 2, 4, 8, 12, and 16 weeks to assess efficacy and safety. Colonization with *L. crispatus* CTV-05 and other lactobacilli, as well as *E. coli*, will be assessed at all visits. Nugent scores will be determined at baseline and all subsequent visits to evaluate vaginal microbiota pre- and post-treatment.

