6.5 Early Discontinuations

If a study subject should discontinue the study prior to Visit 6, all end of study procedures and CRFs should be completed.

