10.2 Secondary Endpoints

The secondary endpoints of this study are parameters of vaginal environment and colonization and adverse events due to the study product.

1. Vaginal colonization with total lactobacilli (as assessed by vaginal culture) and *Lactobacillus crispatus* strain CTV-05 (as assessed by rep-PCR) at Visits 1 through 6 in the LACTIN-V group (Group A) as compared to the placebo group (Group B).
2. Vaginal colonization with *E. coli*, in the LACTIN-V group (Group A) as compared to the placebo group (Group B), as assessed by the presence of *E. coli* on vaginal culture at Visits 1 through 6.
3. Shifts in the vaginal microbiota of individual subjects, as assessed by Nugent score of vaginal gram stains at Visits 1 through 6, in the LACTIN-V group (Group A) as compared to the placebo group (Group B).
4. Shifts in the composition of vaginal microbiota, as assessed by qualitative and/or quantitative DNA amplification of stored vaginal specimens from all visits.
5. Presence and/or quantitation of H₂O₂, lactic acid, and cytokine profiles at Visits 1 through 6, in the LACTIN-V group (Group A) as compared to the placebo group (Group B).
6. Safety and tolerability will be evaluated by the number (%) of subjects with any treatment emergent adverse event, reported symptoms and/or abnormal pelvic examination results over the four-month study period.

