10.10 Analysis of Secondary Endpoints

10.10.1 Shifts in Vaginal Microbiota, as Assessed by Nugent score

Significant changes in vaginal microbiota will be evaluated by the Nugent score with shift tables from Visit 1 (Day 1) to Visit 6. The Nugent score is graded as 0 to 10 and categorized as follows:

- 1 Normal, if between 0 and 3;
- 2 Intermediate, if between 4 and 6;
- 3 Bacterial vaginosis (BV), if between 7 and 10.

See Appendix A, Nugent Scoring System for Gram Stained Vaginal Smears, for complete Nugent scoring criteria.

The following shift table will be used to summarize the change in Nugent score from Visit 1 (Day 1) to Visit 6 (or final score).

Table 2 Nugent Score Shift Table

	Final Nugent Score	0–3	4–6	≥ 7	Total
Baseline Nugent Score	0–3				
	4–6				
	≥ 7				

Changes within each group and between groups will be reported.

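### Section 6.3.5 limits the follow-up Nugent smear to Visit 5, against six other places that require it throughout, and section 6.3 has no procedure list for Visit 6

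*Combined protocol and SAP*

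**What the plan says.** Section 6.3 sets out the procedures visit by visit. The Visit 1 list (6.3.4) includes "Vaginal swab for gram stain Nugent score", so a baseline is taken. The follow-up list (6.3.5) opens with "The following procedures and assessments will be performed at follow-up Visits 2 thru 5 (unless otherwise specified", and its item for the smear reads "Vaginal swab for gram stain Nugent score sent to laboratory (Visit 5 only". The next heading, 6.3.6, deals with unscheduled visits. No list for Visit 6 stands between them.

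Elsewhere the smear is scheduled more widely:

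- Secondary objective 4 in 3.2.2: "as assessed by Nugent score of vaginal gram stains at all visits".
- Design rationale, 4.3: "Nugent scores will be determined at baseline and all subsequent visits".
- Laboratory testing, 6.9.2: the Gram stain is marked for all visits.
- Secondary endpoint 3 in 10.2: "as assessed by Nugent score of vaginal gram stains at Visits 1 through 6". Section 10.3 gives the same range.
- Study procedures flow chart: the Gram stain swab is marked at every visit from Visit 0 to Visit 6.

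The planned analysis in 10.10.1 evaluates the score "with shift tables from Visit 1 (Day 1) to Visit 6", and Table 1 of section 10.8 names the same two visits with a CMH method. Section 10.10.1 then allows a final score in place of Visit 6, and Table 2 labels that axis as the final score.

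**The concern.** The restriction to Visit 5 is a stated rule, so a reader cannot treat it as a gap to be filled from the flow chart. Two instructions for the same swab oppose each other, and the protocol gives no order of precedence between the visit lists, the laboratory section and the flow chart. Staff who work from section 6.3 would be following the protocol while failing to collect part of a secondary endpoint. Vaginal smears are tied to the day of the visit and cannot be reconstructed later.

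Visit 6 is exposed in a different way: section 6.3 is silent on it. Yet Visit 6 is the planned end of the Nugent shift, and section 9.1 makes it the close of data for all analyses.

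**Working it through.** The plan states no figure on this point, so the check sets the schedules side by side and counts visits. Weeks are those of 10.3 and the flow chart.

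| Visit | Section 6.3 lists | 6.9.2 and flow chart | 10.2 and 10.3 | Role in the 10.10.1 shift table |
|---|---|---|---|---|
| 1 (randomization) | yes | yes | yes | baseline |
| 2 (Week 3) | excluded | yes | yes | none named |
| 3 (Week 6) | excluded | yes | yes | none named |
| 4 (Week 10) | excluded | yes | yes | none named |
| 5 (Week 14) | yes | yes | yes | only as a substitute final score |
| 6 (Week 18) | no list | yes | yes | planned final score |

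1. Required post-baseline scores per woman: Visits 2, 3, 4, 5 and 6, which is 5.
2. Lost if 6.3.5 is obeyed: Visits 2, 3 and 4, which is 3 of 5. With the 276 women of 4.3 and 5.1 and full retention, 276 × 3 = 828 of 276 × 5 = 1,380 smears. With the 250 women of 10.4, 250 × 3 = 750 of 1,250.
3. Lost if the Visit 6 smear is missed as well: 4 of 5. That is 276 × 4 = 1,104 of 1,380 (or 1,000 of 1,250), leaving only Visit 5.
4. Effect of step 3 on the shift table: the final score would come from Week 14. That is 18 − 14 = 4 weeks earlier than planned. Section 4.3 gives different return weeks (2, 4, 8, 12 and 16). On that schedule Visits 5 and 6 fall at Weeks 12 and 16, again 4 weeks apart.
5. What the surviving smears describe: the protocol states two lengths of weekly dosing, 8 weeks (3.4.1, 5.1) and 10 weeks (4.1, 4.2, 10.1, flow chart), which themselves need reconciling. If weekly doses start on Day 8 as in 4.2, the last scheduled dose falls on Day 8 + 7 × 7 = Day 57 or Day 8 + 7 × 9 = Day 71. Visit 5 comes after both. Under 6.3.5, therefore, no post-baseline Nugent score would be taken during scheduled dosing.

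The other vaginal samples are less affected. Section 6.3.5 keeps the cultures, rep-PCR and stored DNA swabs at Visits 2 to 5. For those the only gap in section 6.3 is Visit 6.

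**The case against.** The strongest reply is that six places agree and one does not. The flow chart is a complete schedule that coordinators commonly use, so the smears would probably be taken. Nothing ranks 6.3.5 above the flow chart, and the case report forms are not in view. That stands, and it makes the loss conditional on which instruction staff follow. It does not remove the contradiction.

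Three stronger readings are tempting, and the documents do not support them:

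- A reader might infer that the list rules out a Visit 6 smear. It does not: 6.3.5 ends at Visit 5 and says nothing about Visit 6. A site with only section 6.3 would have no instructions for Visit 6 at all and would have to turn to the flow chart or 6.9.2, both of which call for the Gram stain.
- A reader might infer that the shift table would be empty. The final-score allowance in 10.10.1 means that Visit 5 values would fill it.
- Section 6.5 says that when a woman leaves "prior to Visit 6, all end of study procedures and CRFs should be completed", and a reader might infer that those procedures are listed nowhere. The flow chart's Visit 6 column lists them. Sections 4.4.2 and 5.1 (pelvic examination) and 6.9.1 (pregnancy test) support it. What is missing is a list in section 6.3.

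It is also fair to say that no specified Nugent analysis names Visits 2 to 4, so the planned comparison would be largely unchanged by their loss. One qualification applies. If the final score means the last one available, a woman lost before Visit 5 without an end-of-study visit would have had her final score from one of those visits. The documents give no drop-out rate, so the number cannot be stated.

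**Conclusion.** The contradiction is real and its reach is limited. A site that follows 6.3.5 would not take the Nugent smears at Visits 2, 3 and 4, which is 3 of the 5 post-baseline scores that secondary endpoint 3 requires. Visit 6 is not excluded, but its working instructions sit only in the flow chart and section 6.9. If that smear were also missed, the planned Week 18 shift would become a Week 14 shift.

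This rests on two assumptions: that some staff work from the section 6.3 lists, and, for the smear counts, that retention is complete. Only a secondary endpoint is affected. The point is a modest one, worth correcting because the data cannot be recovered and the correction is cheap.

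**What to change.** 1. In 6.3.5, delete the parenthesis that limits the Nugent smear to Visit 5, so that the item agrees with 6.9.2, 10.2 and the flow chart.
2. Either extend the 6.3.5 list to Visit 6 or add a separate Visit 6 list that carries over the flow chart's Visit 6 column.
3. In doing so, mark the full pelvic examination and the scheduled urine pregnancy test as Visit 6 items. If the list were only retitled, its item 4, which makes the pregnancy test conditional on clinical indication, would conflict with 6.9.1 and the flow chart at Visit 6.
4. In the same pass, reconcile Visit 0. The flow chart marks a Gram stain and vaginal cultures there, and the 6.3.3 list has neither. This does not touch the Visit 1 to 6 endpoint.

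The cost is protocol wording. For Visits 2 to 6 the flow chart already schedules every smear, so no procedure or analysis is added.
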